supervision from [name], attendance of workshops on anxiety treatment, and been involved in the development of *Anxiety Coach*. [name] will train the intervention specialists in the procedures outlined in the UPM for supporting therapists, meet weekly for supervision, and provide additional supervision as needed for concerns about a therapist's use of the study interventions or a patient's progress, clinical deterioration, or development of new symptoms.

C.7.g. Assessment Timeline. Patient participants will receive two assessments conducted via videophone by a trained independent evaluator blind to condition under the supervision of [name]. The initial assessment will be conducted at baseline (Time 1) when the patient's eligibility is determined. The patient will begin treatment within one to two weeks. The patient's response to treatment will be assessed 12 weeks (+/- 2 weeks) after the initial treatment session (Time 2). The evaluations will be comprehensive in nature (e.g., diagnostic interview, clinician ratings, parent- and self-reports). Accommodations will be made for families without electronic access, such as videophone assessments in the therapist's office. Beginning at the baseline assessment and continuing throughout the study, patients will rate their daily symptoms with an iPod Touch. Therapists in Trial 1 will complete the survey materials from Phase I inquiring about treatment practices and beliefs prior to receiving training in the use of *Anxiety Coach*. Two weeks after receiving *Anxiety Coach* training the therapists will be asked to complete the same survey material plus measures assessing software usability. 6 months after the initial training, therapist will be asked to complete the survey material, usability measure, and a questionnaire about their actual use of *Anxiety Coach* since the training.

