C.7.h. Additional Treatment. During Trials 2 and 3 participants will be asked to refrain from participating in additional treatment during the study (i.e. other therapy, initiating or changing medications). Following the post-treatment evaluation patients can continue with their therapist or seek other treatment. Patients in the TAU condition will be provided *Anxiety Coach* and treatment recommendations after the post-treatment evaluation. Given that many children are treated with medication before being referred for therapy, restricting participation to medication-free patients would interfere with enrollment. Medication changes during the study will be recorded and analyzed.

C.8. Procedural Considerations.

C.8.a. Age Range. A relatively broad age range will be included to evaluate the feasibility of utilizing *Anxiety Coach* with children at different developmental levels. Although the proposed agent of change (cognitive change through exposure) is theoretically consistent across the age range, therapists will be allowed freedom to administer these techniques in a developmentally sensitive manner, e.g. allowing more independence with adolescents, less discussion of cognitions with children. The current proposal focuses on youth as this population is at particularly high risk of not receiving effective treatment, has an high level of familiarity with ICT, and has been found to be particularly motivated by the introduction of ICTs into treatment.^{4,27,28}

C.8.b. Inclusion of Patients with Comorbid Disorders. Children with multiple anxiety disorders or additional diagnosis (i.e., well-managed ADHD) will be included except disorders that present a more severe group requiring treatment that might interfere with CBT (e.g., Major Depression, Oppositional Defiant Disorder).

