More generally, the study includes potential risks related to psychotherapy. In rare cases psychotherapy may exacerbate symptoms. Should a patient's symptoms increase significantly anytime during the study and require discontinuation of study treatment, families will be connected with appropriate alternative treatments outside the study protocol including psychotropic medication, additional psychotherapy, or hospitalization. In addition, as with all treatment, the therapists will closely monitor the patient's emotional well-being and pace therapy appropriately (i.e., recommending a slower pace or "exposure breaks"). The therapists will also monitor parent-child interactions and the parent's emotional state to determine if further action is indicated. Moreover, the study therapists will have access to the intervention specialists in all conditions as an additional resource for protecting patients against harm.

The confidentiality of therapists, in addition to patients (children and caregivers), will be maintained through the procedures described above in Section 4.1.1.b. To minimize risk, identifiable information from the survey will only be available to the SRC. However, therapist's inclusion in the pool of providers eligible for participation in Phase II implies an endorsement of openness to CBT and infrequent use of exposure. However, this is thought to pose a limited risk as previous research suggests such responses will be the norm. During recruitment, the structure of phone screenings will allow therapists to decline participation in a manner that does not imply a history of disciplinary action.

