Thorough screening and assessment will aim to rule out psychiatric conditions in children and caregivers that may prevent families from participating in the study. Once in the study families will be followed closely by a therapist and an intervention specialist with considerable experience providing treatment for childhood anxiety disorders under the supervisor of [name]. [name], the treating therapist, an intervention specialist or a covering clinician through the Mayo Clinic Division of Child Psychiatry and Psychology will be available for research subjects 24 hours a day, 7 days a week. Side effects and adverse events will be monitored closely throughout the study. Specifically, the therapists (or evaluator) will conduct a general inquiry at each contact regarding symptomatology, adverse events, self-harm, or any health complaints. If at any point during the study participants develop elevated risk for harm to self or others, or experience increased symptoms, appropriate treatment will be instituted. Reported complaints will be coded on a standardized form as Mild (minor complaint causing no interference and not requiring intervention), Moderate (more than minimal problem, source of some interference and may require intervention), Severe (significant complaint, definite interference requiring intervention), or Serious (life threatening, a potential for long-term disability, and/or requiring hospitalization). Based on the nature of the complaint the independent evaluator will determine whether it is related to the study, and [name] will take appropriate action (e.g., monitoring, adjunctive intervention, removal from study). Any cases of suspected abuse will be reported consistent with the roles of mandated reporters by the therapist and study staff in conjunction with [name]. Any instances of suspected malpractice by study therapists will be addressed consistent with institutional guidelines, the ethics code of the American Psychological Association, and the credentialing body of the therapist in question.

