In cases where children are receiving anxiety-related medications prior to the period of study eligibility, or where initiation (or discontinuation) of a medication during the study period seems clinically necessary, this care will be managed by prescribing physician. Although we expect that medication changes will be minimal or absent, if such occur, we will analyze outcomes from patients with and without medication changes occurring during the course of the study to determine if changes in outcomes are attributable to medication changes.

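### Comparing patients with and without an on-study medication change cannot show that outcomes are due to medication, because changes follow the child's clinical course

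*Protocol*

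**What the plan says.** The analysis is stated near the end of Protocol section 4.1.2.b: "we will analyze outcomes from patients with and without medication changes occurring during the course of the study", and its purpose is "to determine if changes in outcomes are attributable to medication changes". The preceding sentence covers cases "where initiation (or discontinuation) of a medication during the study period seems clinically necessary" and leaves that care to the prescribing physician. The protocol adds that "we expect that medication changes will be minimal or absent".

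Other places bear on why a change happens:

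- Section 4.1.1.c: if symptoms rise significantly and study treatment has to be discontinued, families are connected with "alternative treatments outside the study protocol including psychotropic medication, additional psychotherapy, or hospitalization".
- Section 4.1.2.b: if participants reach elevated risk of harm or "experience increased symptoms, appropriate treatment will be instituted". It also lets investigators recommend adjunctive treatment when a patient deteriorates.

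On method, section C.7.h says only "Medication changes during the study will be recorded and analyzed", and C.4.b says much the same. The SAP mentions no medication analysis.

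**The concern.** The stated purpose is causal, but the comparison is observational. Whether a child's medication changes is decided after randomization, by clinicians responding to how the child is doing. How the child is doing also predicts the end-of-study score. The two groups would therefore be expected to differ at the end even if the medication did nothing. This is confounding by indication, and the protocol's own description of when changes occur documents it.

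The study is meant to supply estimates for a later, fully powered trial. If the comparison is read as its wording invites, a difference between changers and non-changers could be taken as a medication effect, and the absence of one as evidence that medication did not matter. Neither conclusion follows from the analysis.

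**Working it through.** The plan gives no figure for this analysis, so there is nothing to reproduce. The check has three steps.

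**1. Does any text remove the confounding?**

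- Section C.10.b.2 has an ANCOVA controlling for diagnosis and symptom severity, but it applies to therapists' use of exposure.
- Section C.7.g says "Patient participants will receive two assessments conducted via videophone", at baseline and about 12 weeks, so no formal assessment records the child's state just before a change. Daily ratings are collected, but no text uses them to adjust for course before a change.
- No passage defines groups by the timing or reason of a change, or names a comparison model.

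Nothing corrects the inference.

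**2. How large could a spurious difference be?**

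From the documents: 30 patients in each of Trials 2 and 3 (Aim 2), 60 in total (section 4.1.1.a). Assumed, because the documents do not say: medication effect zero; outcome SD 1; correlation ρ of 0.4 to 0.6 between mid-course and end severity; a share p of 10% to 20% changing; changes going to the children who score worst on mid-course severity plus noise of equal variance. The trigger score then correlates 1/√2 = 0.707 with mid-course severity.

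Large-sample difference, changers minus non-changers: ρ × 0.707 × φ(z) / [p(1 − p)], where φ(z) is the normal density at the cut-off for the worst p.

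| p | φ(z) | φ(z)/[p(1 − p)] | ρ = 0.4 | ρ = 0.6 |
|---|---|---|---|---|
| 0.10 | 0.1755 | 0.1755/0.09 = 1.95 | 0.55 SD | 0.83 SD |
| 0.20 | 0.2800 | 0.2800/0.16 = 1.75 | 0.49 SD | 0.74 SD |

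Simulation at the actual sample sizes under the same assumptions gives 0.48 to 0.80 SD. If a two-sample t-test at 0.05 were applied, it would reject in about 13% to 35% of trials with 30 patients and 23% to 65% with 60 pooled.

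These results depend on the assumptions:

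- With ρ of 0.3 to 0.7 and a less noisy trigger (noise SD 0.5), the difference runs from 0.45 to 1.19 SD.
- With one changer, the worst-scoring child, a t-test would reject in about 8% to 13% of trials with 30 patients and 10% to 15% with 60.
- With changers split evenly between the worst- and best-scoring children, the two tails cancel. The mean difference is about 0 and rejection is about 3% to 5%.

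**3. Would it be informative without confounding?**

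Difference detectable with 80% power: (1.96 + 0.84) × √(1/k + 1/(N − k)), with k changers among N patients.

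- 3 of 30: 2.80 × √(1/3 + 1/27) = 1.70 SD.
- 12 of 60: 2.80 × √(1/12 + 1/48) = 0.90 SD.

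Power for a true 0.5 SD effect is 0.13 and 0.34 respectively. Even an unconfounded comparison would settle little.

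**The case against.** The case for leaving the plan alone has real weight.

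- **Scale.** Few or no changes are expected, they are discouraged (C.4.b, C.7.h), and patients with a recent antidepressant or antipsychotic change are excluded at entry. Section C.10.a calls the analysis primarily descriptive and the study unpowered; C.10.b.2 calls group tests exploratory. This stands and limits the consequence. It does not make the comparison causal: exploratory status concerns error control and power, not confounding.
- **No test is specified.** Section 4.1.2.b names no test or threshold. This stands, so the rejection rates above are illustrative and are not properties of a planned procedure.
- **Direction.** A reader might infer that the comparison will make patients with changes look worse. The documents do not support that. The protocol's wording also covers discontinuation, which may follow improvement or side effects, and the mix is not stated. This removes any claim about the sign of the bias. It does not rescue attribution, since a bias of unknown sign is no easier to read through.
- **The arm comparison.** A reader might also infer that this analysis would displace or modify the randomized result. No text says so. Section C.10.c makes intention-to-treat the principal analysis set, and 4.1.2.b includes all randomized participants in the analyses.

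**Conclusion.** The stated purpose is wrong as written: the planned comparison cannot determine whether outcomes are attributable to medication changes. That conclusion rests only on the protocol's account of when changes occur and on the absence of any adjustment for prior course. It does not depend on the simulation.

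The size is uncertain. The illustration of about 0.5 to 0.8 SD holds only if every change follows worsening, with the assumed change rate and correlation; an even mix of worsening and improving children takes it to about zero. The fault lies in the attribution claim. Recording and describing medication changes is sound. The practical consequence is modest, because the analysis is secondary, arises only if changes occur, and sits in a feasibility pilot.

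**What to change.** In Protocol section 4.1.2.b, delete the attribution purpose. In its place:

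1. Report the number, type, timing and reason of medication changes by randomized arm.
2. State that the intention-to-treat comparison already planned in C.10.c, regardless of medication change, remains the main result.
3. If changes occur, show the randomized-arm comparison with and without the changers as a descriptive sensitivity analysis. State that it is not read as a medication effect, since leaving changers out is itself a selection after randomization.

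More elaborate handling, such as setting outcomes after a change to missing and imputing them, or counting every change as non-response on the CGI-I, is debatable with so few patients. The first discards observed data. The second would misclassify a child whose medication was stopped because of improvement.

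The cost is two sentences of wording and one extra run. The changes are already to be recorded; the reason and timing need to be captured with them.

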4.1.3 Potential Benefits of the Proposed Research to Human Subjects and Others

Participants in the study potentially will benefit from receiving a comprehensive psychiatric evaluation and treatment for childhood anxiety and access to a novel treatment aide (either during or after the study period in the treatment as usual condition). Although this study is designed to develop the treatment, rather than demonstrate efficacy, participants will likely experience improvement in symptoms and functioning. In addition, the patients will be compensated \$25 for pre-assessment and \$25 for post-assessment (total of \$50) and the therapists will be compensated up to \$75 per patient, up to 3 patients. The patient and therapist will be able to keep the iPod Touch. Benefits to others are discussed in Section 4.1.4.

4.1.4 Importance of the Knowledge to be Gained

The primary benefit to society is the creation of a novel tool for 1) disseminating evidenced-based treatment for childhood anxiety disorders to practitioners and 2) providing effective care to children who have limited access to brick and mortar mental health facilities. Anxiety disorders are the most common psychiatric disorders in childhood with prevalence rates as high as 15%, but the least likely to be treated (approximately 30%).¹⁻⁴ If left untreated or inadequately treated, these disorders cause substantial impairment across a variety of domains of functioning, are highly co-morbid with other disorders, and often persist into adulthood.⁵⁻⁸ In addition to improving the lives of children with anxiety disorders and their families, increased access to treatment has a benefit for society as a whole by decreasing the health-related costs of anxiety disorders.

Although a wealth of data supports the efficacy of cognitive behavioral therapy (CBT) for childhood anxiety disorders,^{30,49-51} efforts to transport these interventions into clinical settings have been largely unsuccessful.^{18,52-54} The poor performance of efficacious interventions in clinical settings is likely due to the infrequent use of exposure.^{14,15} The low rate of exposure stands in stark contrast to the emphasis on this procedure in manualized treatments and the general scientific consensus regarding its importance.^{29,55-58,61,62} By developing a tool for disseminating and providing CBT with minimal direct contact, the current study will increase access to evidence-based care for children who have previously been deprived of effective treatment. More broadly, the tools developed in this proposal may be adapted to increase the efficiency, generalizability, and durability of treatment for other psychiatric disorders.

The mobile device-based treatment and supporting protocol will be considered the products of this grant. To date, no such application with data supporting its effectiveness exists to disseminate or provide CBT with minimal direct contact for childhood anxiety disorders. By completing the pilot RCT in Phase II and revisions in Phase III, the investigators will be well-positioned to pursue funding for further evaluation of the treatment. This line of research has the potential to inform research into the development of similar approaches for other psychiatric disorders. To maximize the translational value of the current study the scientific results and the treatment protocol will be prepared for publication. In addition, the data gathered from this project will form the basis of an application for R01 funding to investigate the efficacy and cost-effectiveness of the intervention in a fully powered clinical trial.

4.1.5. Data and Safety Monitoring Plan

The treating therapist, an intervention specialist, and [name] will closely monitor participants once they have been enrolled in the study. Therapists will monitor patient symptoms and safety as part of clinical care through face-to-face sessions or the web-portal depending on the condition. The therapists and intervention specialists will review the patient progress and safety on a weekly basis through the daily ratings available in the web-portal. [name] will supervise all study activity and be responsible for all data and safety monitoring. Monitoring will consist of weekly meetings with intervention specialists, independent evaluators, and the project director to review all active participants and data collected via telephone screenings, assessments, the web-portal, session recordings, and therapist reports. All adverse events will be reviewed and reported by [name] with the assistance of the project director to the IRB. The IRB will also monitor data and safety through annual progress reports. Drs. [name] (with consultation from Drs. [name], [name], and [name]) will review data at the end of the open trial and pilot RCT to assess the appropriateness of each treatment and review any adverse events. As noted in Sections 4.1.1.b. the confidentiality of research data will be closely guarded through separating identifying information from patient responses and storing all data in locked or password protected locations. [name] has overall responsibility for monitoring the integrity of the study data and patient safety under the oversight of the IRB. [name] will be responsible for reviewing and reporting to the IRB plans for data and safety monitoring, reviewing adverse event reports, monitoring data integrity during the study, and interpreting the relevance to the study of any external scientific or therapeutic developments.

The following procedures will be followed to ensure participant safety: a) Participants at increased risk for adverse events will be excluded from the study (e.g., actively suicidal, psychosis, below age 7); b) Participants' symptoms will be closely monitored throughout the study by the treating therapist, intervention specialists, and [name]; c) Participants will be offered additional, emergent treatment as needed; d) the study staff will meet weekly to discuss participant safety; and e) The adequacy of safety procedures and the safety of participants will be monitored by the IRB.

The following procedures will be followed in reporting adverse events: All adverse events occurring during the study, including those not meeting the criteria of an Unanticipated Serious Adverse Event (USAЕ) will be recorded on the appropriate case report form. Records of these events will be maintained and reports submitted to the IRB according to the regulatory requirements. Expected serious adverse events (SAEs) and nonsignificant (not serious) adverse events (AEs) will be reported to the IRB at the annual review. Expected adverse events and anticipated adverse device effects are those listed in the protocol, investigational device information, or consent documents as a potential risk factor. USAEs will be reported to the IRB within five working days of learning of it using the Reportable Event form in the IRB electronic system.

BIBLIOGRAPHY

3. Service USPH. *Report of the Surgeon General's Conference on Children's Mental Health: A National Action Agenda*. Washington, DC: Department of Health and Human Services; 2000.
8. Anderson JC. Epidemiological issues. In: [name] TH, King NJ, Yule W, eds. *International handbook or phobic and anxiety disorders in children and adolescents*. New York: Plenum Press; 1994:43-65.

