C.5.e. Treatment as usual (TAU). The control condition in Trial 3 will consist of having the family participate in the existing clinical services offered by the therapist over the 12-week period. After 12-weeks they will be asked to sign a release of information to have the any outside treatment records sent for review by the study staff. The records will be coded for treatment components. As the post-study evaluations, patients in the TAU condition will receive Anxiety Coach and be offered additional treatment as needed.

C.6. Design Considerations

C.6.a. Justification of Experimental Design. The use of three conditions across two trials allows for an examination of the effects of *Anxiety Coach* and direct therapist contact. Specifically, the **TAU vs. FTF-AC comparison** provides an estimate of the feasibility and palatability of *Anxiety Coach* to therapists, a measure

of the extent to which the application facilitates therapists' use of exposure-based methods, the usefulness of *Anxiety Coach* for disseminating evidence-based CBT methods to community therapists, and its value for facilitating treatment adherence among patients with anxiety disorders. Randomizing therapists/patients to one of two conditions removes the potential for bias to affect recruitment, keeps the evaluators blind to experimental condition, removes concerns with order effects, and allows for the more patients to be treated simultaneously thus decreasing the length of the study. **The MC-AC vs. TAU comparison** provides an estimate of the feasibility as well as the impact on acceptability and outcome of using *Anxiety Coach* with limited direct therapist contact as a method for extending treatment outside of the brick and mortar mental health settings. To increase the real-world generalizability of the study, the study will not pay for therapy, but patients in all conditions will be reimbursed for participation in assessments and will be allowed to keep the iPod Touch.

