C.7.d. Consent and Evaluation. For Trials 2 and 3 the videophone consent and evaluation visit should be completed within 1 week (+/- 1 week) from the initial therapist visit and will be organized into two parts: 1) Consent and 2) Evaluation. During the Consent phase, the consent/assent documents will be reviewed and all parties will be given adequate opportunity to ask questions. Specific areas of the consent/assent will be re-reviewed if deficits in understanding are identified. If consent/assent is signed, completion of the Evaluation phase of the visit will commence. If signed consent/assent is not received, the patient will not be enrolled and the information will not be used. Patient eligibility will be formally determined during the Evaluation phase by an independent evaluator blind to the therapy condition under the supervision of [name]. At this time the child and parent will complete paper and pencil measures as well as interviewer administered structured diagnostic interviews. The feasibility of conducting assessments via videophone has been demonstrated in a recently completed multi-site study of an intensive treatment with 20 children diagnosed with OCD coordinated by [name]. In this study 100% of the OCD diagnoses made at the initial evaluation via videophone were confirmed with face-to-face assessments completed after a one-month no-treatment period. Preliminary data suggest that 67% did not meet criteria for OCD after the evaluation and scores on interview administered continuous measures decreased by 65% suggesting that videophone assessments are sensitive to treatment. Access to ICT did not appear to harm recruitment as 100% of the families who expressed interest in participation already had access to the Internet prior to study enrollment. At the end of the videophone evaluation, caregivers will be instructed to return signed copies of consent/assent forms and completed parent- and child-report forms in the postage-paid envelope to study staff as soon as possible. Patients will not be considered enrolled in the study until the signed consent/assent documents have been received and signed by study staff. Patients for whom consent/assent is not returned will be considered screen failures, and data collected prior to receiving consent will not be included in any research-related activities.

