C.9. Description of Assessment Measures. In Trial 1 therapists will complete study measures before training, two weeks after training, and then six months later. In Trials 2 and 3, all study measures will be completed at pre- and post-treatment assessment periods except as noted below. Independent evaluators under the supervision of [name] blind to study condition will administer clinician-rated instruments. Therapist, parent and child report will be completed online via the Survey Research Centers electronic survey tools (or by paper and pencil and return via mail if completion electronically is not available).

C.9.a. Clinician-Administered Measures: Anxiety Disorders Interview Schedule for DSM-IV-Child Version Child and Parent Interview Schedules (ADIS-IV-C/P).⁷⁹ The ADIS-IV-C/P are structured interviews to assess the child's symptoms. Diagnoses reflect endorsement of symptoms as well as a severity rating (patient impairment/distress) of at least 4 on a 0-8 scale. The ADIS-IV will be administered in its entirety to the child and the parent together at pre- and post-treatment to determine whether an anxiety disorder is the primary diagnosis and the presence of comorbid diagnoses. Pediatric Anxiety Rating Scale (PARS).⁸⁰ The PARS is a summation of six items assessing anxiety severity, frequency, distress, avoidance, and interference and has been used as the primary continuous outcome measure in treatment studies.³⁰ Clinical Global Impression-Severity and Improvement (CGI-S/I).⁸¹ The CGI-S/I is a 7-point clinician rating of severity of psychopathology and treatment response. The CGI-I will be completed at time 2 and youth receiving a score of 1 ("very much improved") or 2 ("much improved") will be considered treatment responders. Finally, the child and parents will be asked to rate the recent severity of the child's anxiety symptoms on a 0 to 10 scale.

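### The weekly monitoring meetings in Protocol 4.1.5 include the independent evaluators and review data that can reveal treatment arm, which conflicts with the promised blinding of the ADIS, PARS and CGI raters in Trials 2 and 3

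*Protocol*

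**What the plan says.** **The blinding promise.** Protocol C.7.g gives each patient "two assessments conducted via videophone by a trained independent evaluator blind to condition", at baseline (Time 1) and about 12 weeks after the first treatment session (Time 2). C.9 says for Trials 2 and 3 that evaluators "blind to study condition will administer clinician-rated instruments"; C.9.a lists these as the ADIS-IV-C/P, the PARS and the CGI. C.7.d has eligibility decided "by an independent evaluator blind to the therapy condition". C.6.a counts it among the merits of randomization in Trial 2 that it "keeps the evaluators blind to experimental condition".

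**The monitoring plan.** Section 4.1.5 describes "weekly meetings with intervention specialists, independent evaluators, and the project director to review all active participants and data collected". The sources are "data collected via telephone screenings, assessments, the web-portal, session recordings, and therapist reports". The same section says therapists monitor patients "through face-to-face sessions or the web-portal depending on the condition".

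**The session coder.** C.9.h assigns the coding of recordings to a separate evaluator who is blind to the hypotheses and to assessment results. Section 4.1.1.b gives the coding to the independent evaluators as a group, and says that they also collect and enter all other data.

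**The concern.** The PARS, the CGI and the post-treatment diagnosis are judgement ratings. Therapists know which treatment they give, and patients come to know which they receive. Blinding the rater is therefore the main protection against detection bias for these measures. If the raters sit in a weekly review of how each active patient is being treated, they can learn the arm before they rate that patient at Time 2.

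What is at stake is the between-group contrast in symptom change. C.10.b.2 compares it in Trials 2 and 3 with the aim of generating effect estimates, and says the analyses are to help plan a fully powered trial. Application use, exposure coding, usability, satisfaction and the parent and child reports do not depend on the symptom raters' blind.

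**Working it through.** The plan gives no figure to reproduce, and the documents contain nothing from which a bias could be estimated. The check sets the sections side by side.

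**1. Does the blind extend to Time 2?** Yes. C.7.e speaks only of the time of enrollment, but C.7.g covers both assessments and C.9 covers the clinician-rated instruments at pre- and post-treatment.

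**2. Who attends, and about whom?** Section 4.1.5 names independent evaluators without separating symptom raters from session coders. All active participants are reviewed, which includes patients who have not yet had Time 2.

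**3. Can the reviewed data reveal the arm?** The five sources in 4.1.5 are:

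| Source | What it can disclose |
|---|---|
| Telephone screenings | Collected before treatment; not arm-revealing in themselves |
| Assessments | What C.9.h says the session coder must not see |
| Web-portal | Exposure logs and patient messages (C.3.a.1) |
| Session recordings | FTF-AC sessions in which progress is reviewed in the portal (C.5.c) |
| Therapist reports | Content and setting of treatment |

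Three of the five come from treatment delivery.

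- TAU patients get Anxiety Coach and "treatment recommendations after the post-treatment evaluation" (C.7.h). Exposure logs or portal messages before Time 2 therefore point to an Anxiety Coach arm.
- In Trial 3 the treating staff also differ by arm: MC-AC is given by study staff, and TAU by other therapists in the community or within Mayo Clinic (C.3.b).
- Daily ratings alone need not reveal the arm, because Trial 2 TAU patients record them too (C.5.b).
- The route differs by trial. C.9.f specifies audio recording for TAU and FTF-AC, and Trial 3 TAU is coded from records released after 12 weeks (C.5.e). C.7.f, however, says all sessions and communication in every condition of both trials are recorded. In Trial 3 the main routes are portal data and therapist reports.

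**4. Is there a safeguard elsewhere?** No section describes separate meetings, masked summaries, or evaluators leaving for some items.

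**5. Test each reading of the attendee list.**

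- Symptom raters attend: C.7.g and C.9 are contradicted.
- Only session coders attend: the review of assessments contradicts C.9.h.
- Both attend: both blinds are at risk.

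**6. Do other sections keep the roles apart?** C.9.h does. Section 4.1.1.b blurs them, and its list of participant materials includes data entered in the application. C.9.h describes the raters only as blind to the hypotheses and does not repeat that they are blind to condition.

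**7. Scope.** Section 4.1.1.a plans 75 children, 15 of them in Phase I: 75 − 15 = 60 in Trials 2 and 3. The measures concerned are the ADIS, PARS and CGI.

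**The case against.** The strongest reply is that the text is ambiguous rather than contradictory. It does not say the meetings are joint. Each staff group could meet the supervisor separately and bring only its own data, in which case neither blind is broken. Section 4.1.5 also says that therapists and intervention specialists do their weekly review through the daily ratings in the portal, which need not reveal the arm. In 4.1.1.b, independent evaluators may be a class label that includes the separate coder.

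Part of this stands. The protocol does not say that every attendee sees every source, and separate meetings are possible. But the protocol does not describe them. The meeting sentence covers portal data without limit, and also recordings and therapist reports, so the daily-ratings sentence does not confine it. The class-label reading of 4.1.1.b is possible; the conflict does not rest on that section.

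A second reply concerns consequence. C.10.a calls the analysis primarily descriptive, and C.10.b.2 calls group tests exploratory. The SAP, written in the past tense, presents symptom measures by patient and condition and specifies no between-group test. This stands as a limit on the consequence. It does not remove the problem: C.10.b.2 still compares symptom change between groups to generate effect estimates, and a descriptive contrast of ratings by condition is open to the same bias. For ratings already collected, rewording cannot restore the blind; the remedy is disclosure.

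**Conclusion.** The concern holds. As written, the weekly monitoring in 4.1.5 and the rater blinding in C.7.g and C.9 cannot both be relied on, and the coder-only reading runs into C.9.h instead. The contradiction is in the plan; the documents do not show that any rater was unblinded.

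The size of any bias is unknown and is not estimated here. The scope is the evaluator-rated measures of the 60 patients planned for Trials 2 and 3. The conclusion rests on two assumptions: that attendees see at least some of the treatment-delivery data listed, and that no unwritten safeguard exists. The exploratory status of the comparisons keeps the consequence limited. The point should be fixed because a key safeguard is affected and the correction is cheap.

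**What to change.** - **Section 4.1.5:** state that evaluators who give the ADIS, PARS and CGI neither attend nor receive reviews of portal data, session recordings or therapist reports; that they pass safety information from their assessments one way to the investigator; and that session coders do not see assessment results.
- **Section 4.1.1.b:** align with C.9.h, so that session coders are separate from symptom raters.
- **C.9.h:** add that symptom raters are blind to condition, to match C.7.g and C.9.
- **Section 4.1.2.b:** reconcile the independent evaluator's role in judging whether an adverse event is related to the study with the blind. This is a real trade-off for the study team, and no solution is proposed here.
- **If ratings are already collected:** report whether raters attended these reviews, and qualify the claim of blinding accordingly.

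**Cost.** Rewording of these sections and a weekly agenda split by item. No new staff are needed, since C.9.h already plans a separate coder. The downside is that outcome raters leave part of the weekly safety discussion (4.1.5, item d). Item b already gives symptom monitoring to the treating therapist, the intervention specialists and the investigator.
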